3.5. Duration of Treatment

Subject participation in the study will be approximately 4 months.

- Screening Period: 1-14 days which includes BPO Pre-Treatment Period: 5 days (up to 7 days)
- On-Study Treatment Period: 11 weeks of daily study drug treatment.
- Follow-Up Period: 4 weeks.

The overall study is expected to last approximately one year

3.6. End of Study

Subjects who complete all study visits through Week 12/Visit 5 will follow up via a telephone visit at Week 16/Visit 6 in order to complete safety follow-up. Subjects who discontinue early (before Week 12) should still have the EOT procedures performed in order to terminate the subject's participation in the study. If the subject will not return to the clinic, efforts to contact the subject must be documented and the subject will be considered lost to follow-up.

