5.1.2. Procedures for Breaking Treatment Codes

In the event of a medical emergency where breaking the blind is required to provide medical care to the subject, the PI may obtain treatment assignment by opening the unblinding envelope for the subject kit. Sponsor recommends but does not require that the PI contact the Medical Monitor before breaking the blind. Treatment assignment should remain blinded unless that knowledge is necessary to determine subject emergency medical care. The rationale for unblinding must be clearly explained in source documentation and on the CRF/eCRF, along with the date on which the treatment assignment was obtained. The PI is requested to contact the Medical Monitor promptly in case of any treatment unblinding.

Blinding of study treatment is critical to the integrity of this clinical study and therefore, if a subject's treatment assignment is disclosed to the PI, the subject will have study treatment discontinued. All subjects will be followed until study completion unless consent to do so is specifically withdrawn by the subject.

Sponsor may independently unblind cases for expedited reporting of suspected unexpected serious adverse reactions.

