6.1.2. Subject Replacement

If a subject is discontinued from the study for any reason other than a dose-limiting toxicity (DLT; see [Section 7.2.1](#)) prior to the completion of Week 2/Visit 3, that subject will be replaced.

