6.3. Assessments for Premature Discontinuation from Study

If a subject discontinues the study prior to Week 12/Visit 5 (for example, as a result of an AE), every attempt should be made to schedule the subject to complete EOT visit procedures (see [Section 10.2](#), Subject Discontinuation).

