7.2. Adverse Event Details

AEs may be either spontaneously reported or elicited during questioning and examination of a subject. All AEs must be recorded on the AE CRF. If known, the PI should report the diagnosis of the underlying illness or disorder, rather than its individual symptoms. Subjects experiencing AEs that cause interruption or discontinuation of study drug or those experiencing AEs that are present at the end of their participation in the study should receive follow-up as appropriate. AEs should be followed to resolution or stabilization (if possible) and, if they become serious, reported as SAEs. If possible, the outcome of any AEs that caused permanent discontinuation or that were present at the end of the study, especially those considered by the PI to be related to the study drug, should be reported.

Information on the medical condition of subjects should begin following the subject’s written informed consent to participate in the study and a medical history should be taken at screening. During any wash out and baseline periods, any changes in the health of subjects should be recorded as changes in medical history unless an event occurred as a result of a study-related procedure and is unanticipated; in such cases, the event should be recorded as an AE and reported to the Institutional Review Board (IRB) as an “unanticipated problem” in accordance with local procedures. Other changes in subject health information becomes AE data when the subject begins dosing with the study drug; therefore, AE data should be collected from the date of the first dose of study drug until the date of the final study visit. These data are considered treatment-emergent AEs.

The PI will instruct the subject to report any AEs that may occur during the study. At each visit, the PI should ask the subject, in non-directive fashion, about any change in the subject’s overall

health status since the previous visit. Optional photographs may be obtained for areas outside of the face, as clinically indicated for the classification and management of AEs.

The PI will assign a CTCAE grade to all AEs (CTCAE Version 5.0, [Appendix 4](#)). The severity of each AE, as judged by the PI, will be recorded on the appropriate AE CRF and will be graded according to the following scale:

Mild - The AE is usually transient and may require only minimal treatment or therapeutic intervention. The event does not generally interfere with usual activities of daily living.

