Non-systemic (local) AEs Grade 3 or higher for which there is no clear alternative explanation of the cause of the AE will also be considered DLTs. Any subject who experiences a DLT, as described above, must discontinue treatment and be scheduled for a final visit. Any DLTs that are Grade 2 or greater systemic AEs must be reported by the PI immediately. If three or more subjects experience DLTs in the study, enrollment in the study will be halted, and a safety review will occur using an independent medical reviewer who will have access to the subject's treatment allocation. This review shall be completed promptly within 10 business days. Subjects who are active in the study will be instructed to withhold study drug applications during the safety review period. If all of the subjects experiencing DLTs (i.e. three or more) are found to be subjects receiving the active NB01 study drug, the independent medical reviewer will provide a written recommendation to the Sponsor to continue the study, discontinue the study or modify the study protocol. The Sponsor is responsible for promptly reviewing the independent medical reviewer's recommendations, accepting or rejecting these recommendations, and determining whether amendments to the protocol or changes in study conduct will be required. The Sponsor will provide the final written decision regarding the study status. In the event this is not the case, the independent medical reviewer will notify the Sponsor and Medical Monitor of how many subject's DLTs were in subjects receiving vehicle (e.g. Y subjects). In the event Y new subjects experience DLTs, the independent medical reviewer review process outlined above will be repeated. This process will be repeated throughout the entire study until the study is complete or

the stopping rule has been met. In the event that a total of three (3) or more subjects experience DLTs related to NB01 study drug, the study will be discontinued.

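### The early-discontinuation sections do not give early leavers the Visit 6 safety call, and Section 5.1.2 leaves it unclear whether they should get one

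*Protocol*

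**What the plan says.** Section 3.6 of the protocol assigns the final safety contact by completion status: "Subjects who complete all study visits through Week 12/Visit 5 will follow up via a telephone visit at Week 16/Visit 6". For the rest, "Subjects who discontinue early (before Week 12) should still have the EOT procedures performed in order to terminate the" subject's participation. If such a subject will not come back to the clinic, "efforts to contact the subject must be documented and the subject will be considered lost to follow-up"; no telephone assessment is mentioned.

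The other sections on early discontinuation agree with 3.6:

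- Section 6.3: "every attempt should be made to schedule the subject to complete EOT visit procedures".
- Section 7.2.1, on dose-limiting toxicity (DLT): "Any subject who experiences a DLT, as described above, must discontinue treatment and be scheduled for a final visit".
- Section 10.2 and Appendix 2 note t call for the Week 12/EOT procedures. Note t wants them done as soon as possible. Neither adds a later contact.

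Section 7.2 sets the AE collection period: "AE data should be collected from the date of the first dose of study drug until the date of the final study visit".

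One sentence points the other way. Section 5.1.2, directly after the rule that a subject whose assignment is disclosed to the investigator stops treatment, says "All subjects will be followed until study completion unless consent to do so is specifically withdrawn by the subject". Section 10.1 defines completion as attending all study visits, and these include Visit 6.

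**The concern.** Safety and tolerability are the primary objective. The product is a live organism meant to engraft, so what happens after the last application matters. Appendix 2 note x gives the Week 16 call two purposes: to learn the outcome of events ongoing at Week 12, and to find new AEs and local skin reactions (LSRs). The sponsor therefore regards active questioning after the last dose as part of the safety assessment, but the sections that govern early leavers do not provide it for them.

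These subjects still count. SAP 8.2.1 keeps everyone who applied study drug in the Safety population, and SAP 8.12.2 reports the percentage of subjects with each treatment-emergent AE. Section 6.1.2 replaces most subjects who stop "prior to the completion of Week 2/Visit 3, that subject will be replaced", but a replaced subject who was treated stays in the Safety population. The AE percentages would then pool subjects with unequal post-dose questioning. A DLT in Section 7.2.1 can be a systemic Grade 2 event, which need not be serious, so the passive rule for serious events would not necessarily pick one up.

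**Working it through.** **Step 1. Reproduce the SAP's last-dose window.** Visit 5 is targeted at Day 80, and dosing stops 3 to 7 days earlier (Appendix 2 note p). Last dose = 80 − 7 to 80 − 3 = Days 73 to 77, which matches SAP 8.8.

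**Step 2. Post-dose observation in completers.** Visit 6 is Day 106 ± 3 = Days 103 to 109 (Appendix 2).

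- Shortest: 103 − 77 = 26 days.
- Longest: 109 − 73 = 36 days.
- At nominal Day 106: 106 − 77 = 29 to 106 − 73 = 33 days.

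Other readings of the windows give other ranges:

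- Last dose always on Day 77: 103 − 77 = 26 to 109 − 77 = 32 days.
- Visit 5 window read as Days 83 to 87, so last dose on Days 76 to 84: 103 − 84 = 19 to 109 − 76 = 33 days.
- Limits of the SAP per-protocol rule (Visit 5 on Days 71 to 90, 1 to 10 days after the last dose), so last dose on Days 61 to 89: 103 − 89 = 14 to 109 − 61 = 48 days.

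**Step 3. Shortfall for an early leaver under Section 3.6 as written.** Let g be the days from last dose to the early EOT visit. The documents do not fix g, so every value below is assumed. Shortfall = (26 to 36) − g. A call 30 days after the last dose would add 30 − g days.

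| g (assumed) | Shortfall against completers | Days added by a 30-day call |
|---|---|---|
| 0 | 26 to 36 | 30 |
| 7 | 19 to 29 | 23 |
| 14 | 12 to 22 | 16 |
| 21 | 5 to 15 | 9 |

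**Step 4. What is already covered after an early EOT visit.**

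| Event | Provision | Gap |
|---|---|---|
| AE that caused stopping, or was present at the end of participation | Followed to resolution or stabilization if possible (7.2, 10.2) | None in principle |
| Serious AE within 30 days of stopping | Reportable if the investigator becomes aware (7.2.2) | Not actively solicited |
| Pregnancy | Subject to report a suspected pregnancy for 30 days after the last application (7.3) | None in principle |
| LSR | Diary dispensed at Visit 5 (6.2.3; Appendix 2 note u); weekly recording through Week 16 (synopsis; SAP 7.2) | Collection after EOT is listed only at Visit 6; no retrieval from early leavers is stated |
| New non-serious AE | None in the early-discontinuation sections | Not solicited after EOT |

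**Step 5. Scale of one missed event.** With 36 subjects split 2:1 (nominally 24 and 12), one subject whose first AE is missed is 1/24 = 4.2 percentage points on NB01 or 1/12 = 8.3 points on vehicle. This is the weight of any single subject. It does not estimate how many events this gap would lose.

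**The case against.** The strongest objection is Section 5.1.2. Taken literally and together with 10.1, it carries every subject who has not withdrawn consent through Visit 6, and those are the subjects at issue here. Even on its narrow reading it covers subjects taken off treatment after unblinding. A reader might infer that the protocol nowhere provides for post-treatment follow-up of early leavers; this sentence means that cannot be said. But it names no visit, day or assessment, it stands in the section on breaking the blind, and on its wide reading it contradicts 3.6, which ends participation at the EOT procedures. A site following 3.6, 6.3 and 10.2 would not make the call. The objection changes the finding from an absence to an unresolved conflict.

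A reader might also infer that LSR recording stops at the early EOT visit. The documents do not support that. The EOT procedures include handing out a diary, and diary LSRs run through Week 16. What is unclear is how an early leaver's diary comes back.

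Two further objections stand. The events of most concern are largely covered (step 4), which leaves mainly new, non-serious AEs. And every shortfall figure for early leavers rests on an assumed interval. The cap at last dose plus 30 days in SAP 8.12.2 should not be cited as a follow-up period either; it only limits imputed AE start dates.

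**Conclusion.** The point holds as a minor one. The sections that govern early discontinuation stop at an EOT or final visit and do not assign the Visit 6 call. Section 5.1.2 can be read to require more, but does not say so clearly. If sites follow 3.6, solicited AE follow-up after the last dose is shorter for early leavers than the 26 to 36 days in completers. That range rests on last doses on Days 73 to 77 and Visit 6 on Days 103 to 109. The shortfall is 19 to 36 days if the early EOT visit comes within a week of the last dose, and less if it comes later.

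The point is confined to treated subjects who can be reached and have not withdrawn consent to contact. It does not extend to deaths, true losses to follow-up, or subjects who refuse contact.

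A reader might infer that the AE comparison between arms is biased. The documents give no dropout figures by arm, so neither the number affected nor the direction or size of any bias can be derived. The safety analysis is descriptive, which limits the consequence further.

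**What to change.** State in Sections 3.6, 6.3, 7.2.1 and 10.2 that every subject who applied study drug and has not withdrawn consent to contact receives the existing Visit 6 telephone assessment (AEs, LSRs, concomitant medications) about 30 days after the last application. Include subjects who will not return to the clinic but can be phoned. Keep AE collection open until that call and retrieve the diary then. Reword 5.1.2 to say whether its follow-up sentence means unblinded subjects or all subjects, and make it agree with 3.6.

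For subjects already closed out, report post-dose observation time (last dose to last AE assessment) by arm in the Safety population, beside the AE percentages. SAP 8.6, 8.8 and 8.12.1 already plan withdrawals with reasons, treatment duration and exposure, so this adds one line to the study report.

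The cost is one protocol amendment with IRB approval (Section 9.2.1), re-consent if the IRB requires a new form, and one call per reachable early leaver. Section 3.3 says that 36 subjects were already randomized, so the amendment may help few subjects or none; in that case the reporting line is the useful part. The call restores only the post-dose period. It does not make up for time on treatment that an early leaver never had.

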3.7. Biomarker Testing

3.7.1. Biomarker Samples to Address the Study Objectives

The following biological specimens may be collected in this study and will be used to evaluate the association of exploratory biomarkers with study drug response, including engraftment, efficacy and/or AEs and to increase knowledge and understanding of the biology of acne or related diseases, and/or the validation of a companion diagnostic for acne. The specific analyses may include but will not be limited to the following biomarkers and assays: cheek swab and Biore® strip TaqMan® and microbial sequencing laboratory analysis. Because biomarker science is a rapidly evolving area of investigation, and AEs in particular are difficult to predict, it is not possible to specify prospectively all tests that will be done on the specimens provided. The testing outlined below is based upon the current state of scientific knowledge. It may be modified during or after the end of the study to remove tests no longer indicated and/or to add new tests based upon the growing state of art knowledge. Any future testing must be approved by local authorities, as applicable, according to specific local regulations.

3.7.2. Biomarker Samples for Optional Future Research

In addition to the study-specific informed consent to be signed by each subject participating in the study, a separate, specific signature will be required to document a subject's agreement to allow the use of the remainder of their already collected microbial biomarker specimens for optional future research, once approved by local authorities, as applicable, according to specific local regulations.

The specimens collected for optional future research will be used to increase our knowledge and understanding of the biology of the study disease and related diseases and to study the association of biomarkers with disease pathogenesis, progression and/or treatment outcomes, including efficacy, AEs, and the processes of drug absorption and disposition. These specimens may be used also to develop biomarker or diagnostic assays and establish the performance characteristics of these assays. The collection and analysis of optional future research specimens will facilitate the rational design of new pharmaceutical agents and the development of diagnostic tests, which may allow for individualized drug therapy for patients in the future.

4. SUBJECT POPULATION

4.1. Number of Subjects and Subject Selection

4.2. Inclusion Criteria

Subjects must meet all of the following inclusion criteria to be eligible for participation in this study.

1. Subject has provided written informed consent.
2. Subject is male or non-pregnant female, 18-40 years of age, inclusive at Screening.
3. Subject has a clinical diagnosis of moderate facial acne vulgaris defined as Grade 3 on the IGA (see [Appendix 3](#), IGA Grading).
4. Subject meets all of the following:
 - A minimum of 20 but not more than 50 facial inflammatory lesions (papules plus pustules), including nasal lesions, and no more than 1 facial nodular lesion (<5 mm)
 - No cystic lesions
 - A minimum of 20 but not more than 125 facial noninflammatory lesions (open and closed comedones), including nasal lesions
5. Female subject with non-cyclical acne.
6. WOCBP willing to use adequate contraception (e.g., total abstinence, IUD, barrier method with spermicide, surgical sterilization or surgically sterilized partner, Depo-Provera®, Nexplanon®, or NuvaRing® for the duration of the Screening Period and during study participation. All oral contraceptive and hormonal implants will need to have been initiated and on a stable dose for at least 3 months prior to the Screening Period. WOCBP are defined as any female who has experienced menarche and who is NOT permanently sterile (hysterectomy, status-post 6 month or more a bilateral tubal ligation or bilateral oophorectomy) or postmenopausal; postmenopausal is defined as 12 consecutive months with no menses without an alternative medical cause.
7. Male subjects willing to use an acceptable method of contraception (e.g., total abstinence, barrier methods with spermicide) during study participation.
8. Subject has the ability to personally apply BPO and study drug, as per protocol.

4.3. Exclusion Criteria

Subjects who meet *any* of the following exclusion criteria are not eligible for participation in this study.

1. Subject has active bacterial, viral, or fungal skin infections.

2. Subject has used any of the following topical anti-acne preparations or procedures on the face:
 - Topical anti-acne treatments including, but not limited to, OTC acne cleansers or treatments, BPO (other than the BPO pre-treatment required during Screening), antibiotics, azelaic acid, dapsone, sulfa based products, corticosteroids, and salicylic acid, within two weeks of Screening;
 - Topical retinoids (e.g., prescription tazarotene, adapalene, and tretinoin, including OTC adapalene) within four weeks of Screening;
 - Light treatments, microdermabrasion, or chemical peels within eight weeks of Screening;
 - Other topical therapy, which may materially affect the subject's acne, in the opinion of the PI.
3. Subject has used any of the following systemic anti-acne medications:
 - Corticosteroids (including intramuscular, intraarticular and intralesional injections) within four weeks of Screening. Inhaled, intranasal, or ocular corticosteroids are allowed if use is stable (stable use is defined as dose and frequency unchanged for at least four weeks prior to Screening);
 - Antibiotics or other systemic anti-acne medications within four weeks of Screening, with the exception of five days or less of antibiotic therapy during this period, but not within one week of Screening;
 - Androgen receptor blockers (i.e., spironolactone or flutamide) within eight weeks of Screening, with the exception of five days or less of spironolactone therapy during this period, but not within one week of Screening;
 - Retinoid therapy (e.g., isotretinoin) within six months of Screening;
 - Vitamin A supplements (greater than 10,000 units per day) within six months of Screening;
 - Other systemic therapy, which may materially affect the subject's acne, in the opinion of the PI.
4. Subject has received any light-based therapies including PDT, blue light, red light lasers, artificial tanning devices within four weeks of Screening and is planning to be exposed to excessive sunlight during the study period.
5. Subject has active nodulocystic acne or acne conglobate, acne fulminans, or other forms of acne (e.g., acne mechanica).

6. Subject has any skin diseases with compromised skin barrier function (e.g. atopic dermatitis, etc.), such as noticeable breaks or cracks in the skin on the face, including severely excoriated skin or skin with open or weeping wounds suggestive of an active infection or increased susceptibility to infection in the treatment area (i.e., face).
7. Subject has facial hair, scarring or other clinical conditions in the treatment area that could interfere with study assessments, in the opinion of the PI.
8. Subject has active clinically significant periodontal disease in the opinion of the PI, or ongoing procedures (e.g., gum grafting).
9. Subject has history/current ocular infections/surgeries within six months of enrollment, with the exception of any history of cataracts.
10. Subject has a history of septic joints/endocarditis.
11. Subject has sensitivity to or difficulty tolerating any ingredients in the study drug, including glycerin, polyethylene glycol.
12. Subject demonstrates non-compliance with BPO pre-treatment during the Screening period. Non-compliance is defined as BPO application for less than 5 days the week prior to Day 1, failure to apply BPO 24-48 hours prior to Day 1, and BPO application within approximately 24 hours of the Day 1 visit.
13. Subject is currently participating in an investigational drug, device, or biologic study or has used an investigational drug, biologic or device treatment within 30 days prior to first application of the study drug.
14. Subjects with prosthetic heart valves, pacemakers, intravascular catheters, or other foreign or prosthetic devices/implantable devices/hardware.
15. Subject has a history of chronic HIV, HCV, or HBV infections.
16. Subject has a history of malignancy (with the exception of non-melanoma skin cancer).
17. Subject is immunosuppressed (such as resulting from transplantation, immunosuppressive therapy, active HIV infection/ AIDS, neutropenia).
18. Subject had a major surgical procedure, open biopsy, or significant traumatic injury within 14 days of initiating study drug (unless the wound has healed), or anticipation of the need for major surgery during the study.
19. Subject has a medical or psychiatric condition and/or history of drug or alcohol abuse that, in the opinion of the PI, makes the subject inappropriate for study inclusion.
20. Subjects with close contacts (e.g., spouses, children, or members in the same household) that have severe barrier defects or are immunocompromised.

21. Subject is unable or unwilling to comply with study protocol procedures.
22. Female subject is pregnant or lactating or is planning to become pregnant and/or breast feed within the duration of study participation.

